Fig. 5. Study Phases: Baseline & Randomization includes 2 Sound Sweeps tests: Test 1 with PBO and \approx 5-7 days later Test 2 with either MEM or PBO. Treatment Phase includes 30 TCT sessions with outcome measures after 10, 20 and 30 sessions. Post-treatment tests assess both immediate biomarker changes and 12-week durability of outcome gains.

Assessments: 30 sessions of TCT will be completed, based on our findings (Fig. 1) and evidence that TCT efficacy is dose-dependent^{25,68,97}. Assessment dates could be based on either: 1. session # (10, 20 and 30 and 12 weeks later); or 2. Time (days) since starting TCT. In our experience^{2,31,34} TCT rates closely match 3/week (30 sessions mean = 65 days; 90% of subjects completed 30 TCT sessions within 11 weeks). Primary analyses will be based on session #, but session dates are recorded and confirmatory analyses will define assessment points based on time passage. Candidate predictive biomarkers are re-tested after session 30.

General Clinical Monitoring: In addition to their established ongoing care, patients are carefully monitored at each session as per our well-established procedures, and through to the week-22 follow-up, for any clinical changes. Each week, a member of our research staff checks vital signs and weight, does a detailed assessment of symptom changes, focusing on psychosis, depression, suicidality and abnormal movements, and tests UTox and pregnancy. A designated unblinded staff member processes UTox results. In the event that a subject tests positive for recreational drugs or a positive pregnancy test, it is promptly reviewed with the on-site Psychiatrist; any “yes” on the Columbia Suicide Severity Rating Scale⁹⁸ (C-SSRS) “Since Last Visit”, or an exacerbation of psychotic symptoms, prompts detailed review, with appropriate clinical interventions. Patients testing positive for recreational drugs will be retested in 1 week; patients with 3 positive tests no longer continue in the study. **Data from subjects who, for this or other reasons, do not complete the full study are carried forward in an “intent to treat” design, and their data are analyzed using linear mixed-effects models.**

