Post-treatment protocol: On completion of 30 TCT sessions, participants will be offered the option of maintaining their assigned drug (PBO or MEM) through the 22-week durability assessments. Those who opt to discontinue the study drug will titrate off, over a 3-week period. After week 22, study blind will be broken, and subjects who continued to receive MEM will again be offered the option of titrating off of MEM vs. maintaining MEM treatment coordinated with, and under the supervision of, their primary provider.

Data Analysis: “Go/No Go” decisions are based on traditional statistical significance (Aim 1) and effect sizes (Aim 2). Formal statistical testing is conducted using linear mixed-effects (LME) models; hypothesis tests are 2-sided ($\alpha=.05$). Model parameters are estimated via the R lme4 package and Cohen’s d is estimated via the

EMAtools package. Type I errors are minimized by constraining the number of primary analyses; secondary analyses use false discovery rate corrections. Expected attrition rates are described above. Because outcome measures involve a “change from baseline”, baseline metrics are compared between PBO and MEM arms, and any baseline differences are addressed in the outcome analyses. Differential drop-out rates from PBO vs. MEM arms are monitored. Data are assumed to be missing at random; full information maximum likelihood estimators are used, and all data/cases are included in analyses. Clinical follow-up is pursued with all patients exiting the study through post-TCT week 12. Cohort differences: For between-subject contrasts (main effect of drug), differences in age, antipsychotic and anticholinergic loads are tested and used as covariates^{2,33,95}. Sex differences are tested for all measures. NIH Data Harmonization: 3 “PhenX Toolkit” (NOT-MH-15-009) measures of function are used; see above and “Resource Sharing Plan”.

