4.4 Statistical Design & Power

Design (see “Research Strategy”, Figure 7): Screened, eligible patients complete clinical, neurocognitive and functional measures and candidate biomarkers. In Test 1, all subjects are tested in Sound Sweeps after PBO, and then assigned to TCT+PBO vs. TCT+MEM arms (n=27/arm) using stratified random sampling (over sex, age and high/low Test 1 (baseline) APS learning) blind to arm identity, similar to¹⁰⁷. Stratifying for baseline APS learning should increase the sensitivity of the primary target engagement metric. An example of a table for arm assignment is seen here:

Gender	Baseline	Age	Group								
Male	High	< 39	PBO	PBO	MEM	MEM	MEM	MEM	PBO	PBO	PBO
	High	≥ 39	PBO	MEM	PBO	MEM	MEM	PBO	MEM	PBO	PBO
	Low	< 39	MEM	MEM	PBO	PBO	PBO	PBO	MEM	MEM	MEM
	Low	≥ 39	MEM	PBO	MEM	PBO	PBO	MEM	PBO	MEM	MEM
Female	High	< 39	PBO	PBO	MEM	MEM	MEM	MEM	PBO	PBO	PBO
	High	≥ 39	PBO	MEM	PBO	MEM	MEM	PBO	MEM	PBO	PBO
	Low	< 39	MEM	PBO	MEM	PBO	PBO	MEM	PBO	MEM	MEM
	Low	≥ 39	MEM	MEM	PBO	PBO	PBO	PBO	MEM	MEM	MEM

Example of table for stratified random sampling, by gender, baseline APS learning (post-PBO) and age (based on approximate mean age (39 yo) of last 100 SZ patients tested in our program)

Test 2 follows approximately 5-7 days later. Tests 1 and 2 are used to assess target engagement (Aim 1: MEM-enhanced APS learning) and MEM effects on auditory discrimination. Our design allows for 20% attrition from enrollment (n=69) to completion of target engagement testing (n=54).

For Aim 2, TCT is scheduled 3 d/week and continues until a subject completes 30-h (approximately 10-12 weeks). 60 min prior to each TCT session, patients take either PBO or 20 mg MEM, as per arm assignment. Patients and staff are blind to study arm; staff are blind to patients’ baseline or post-intervention assessments. Outcome measures are assessed after sessions 10, 20 and 30, and 12 weeks post-TCT. See “Research Strategy” for details.

General Statistical Approach: Hypothesis tests are 2-sided ($\alpha=.05$). Type I error is controlled by selecting optimal *a priori* targets for primary analyses; secondary analyses use false discovery rate corrections. When appropriate, missing data are handled via multiple imputation or full information maximum likelihood estimation. Expected drop-out rates and ways to minimize them are described in the parent application.

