Differential drop-out rates from PBO vs. MEM arms are monitored. Clinical follow-up is pursued with all patients exiting the study through post-TCT week 12.

Cohort differences: For between-subject contrasts (drug), baseline demographic, clinical, antipsychotic/anticholinergic load and performance differences are tested and used as covariates if indicated. Sex differences are tested for all measures.

Procedures for Alternative or Unexpected Results: Linear mixed-effects models allow for the analysis of all available data using an intent-to-treat approach. This approach, however, assumes that data are missing at random. A potential concern is nonrandom dropout, particularly when dropout is related to the (missing) outcomes; that is, not missing at random. To make the missing at random assumption more plausible, we will explore the use of auxiliary variables. Auxiliary variables are covariates that predict both dropout and outcomes. By adding

auxiliary variables to our models, nonrandom dropout is corrected by conditioning treatment effects on the predictors of dropout.

Primary Efficacy Endpoint(s): Aim 1: Target engagement – APS learning will be significantly greater under MEM vs. PBO conditions. Aim 2: Pilot trial - Compared to PBO arm patients, MEM arm patients will exhibit greater clinical benefit, as indicated by one or more of the following: greater, faster or more durable improvements in PANSSt (reduced scores; see below, "Go/No-Go"), MCCBc (increased scores) or WHODAS (reduced scores).

Secondary Efficacy Endpoint(s): Aim 3: Biomarkers - baseline levels of specific neurocognitive or EEG-based measures, or changes in specific measures with initial MEM exposure, predict greater sensitivity to MEM-enhanced neurocognitive, clinical or functional gains over 30 sessions of TCT.

Analyses testing primary and secondary hypotheses will include all subjects' clinical, neurocognitive and functional assessments. Data from subjects who do not complete the full study are carried forward in an "intent to treat" design, and their data are analyzed using linear mixed models. Separate analyses will compare completion / drop-out rates across arms, as well as a 14-item 7-point Likert scale assessing treatment satisfaction.

Go/No-Go decision and primary and secondary endpoints

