"Go/No-Go" decisions are based on traditional statistical significance (Aim 1) and effect sizes (Aim 2). Formal statistical testing is conducted using linear mixed-effects (LME) models; hypothesis tests are 2-sided ($\alpha=0.05$). Model parameters are estimated via the R lme4 package and Cohen's d is estimated via the EMAtools package. Type I errors are minimized by constraining the number of primary analyses; secondary analyses use false discovery rate corrections.

PANSSt scores will be assessed at specific intervals. Because TCT is associated with improvements in both positive and negative symptoms, our *a priori* hypothesis is that a PACT effect will be evident in both positive and negative symptoms. Hence, PANSSt is used as the primary metric of symptomatic gains. A greater reduction in PANSSt score will be detected using data from baseline through TCT 30h, by a significant main effect of group (arm) or a significant interaction of group x session, with post-hoc contrasts revealing significant group differences at TCT 30h. A faster reduction in PANSSt scores will be detected using these same data by a significant interaction of group x session and a significant group difference at a point prior to TCT 30h. A more durable reduction in PANSSt scores will be detected using data from TCT 30h through 12 weeks post-TCT, by a significant main effect of arm or a significant interaction of group x post-TCT day, with post-hoc contrasts revealing significant group differences 12 weeks post-TCT.

Comparable analytic approaches will be used for neurocognition (MCCBc) and function (WHODAS) as described in "Research Strategy". Data will be described as means with SEM. Tests for normalcy will be applied to all data and non-parametric comparisons will be used if normalcy is not demonstrated. The Analysis Set for these data will be all subjects who have completed 30h of TCT and post-TCT clinical, neurocognitive and function assessments. When appropriate, missing data are handled via multiple imputation or full information maximum likelihood estimation.

Secondary regression analyses assess the predictive value of putative biomarkers on clinical, neurocognitive or functional gains from the addition of MEM to TCT. Future studies with larger samples will assess potentially more informative models, e.g. Path Analysis to study moderating effects of APS MEM sensitivity and biomarkers on both indirect (moderated-mediation) and direct paths between treatment and outcome.

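### The carried-forward wording for non-completers can be read as last-observation-carried-forward, which would not fit the likelihood-based handling stated elsewhere

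*Combined protocol and SAP*

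**What the plan says.** Four parts of the combined protocol and SAP bear on patients who stop early.

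- **Research Strategy, Approach, General Clinical Monitoring.** Data from subjects who, for whatever reason, "do not complete the full study are carried forward in an" intent-to-treat design, and "their data are analyzed using linear mixed-effects models".
- **Section 4.4, under Secondary Efficacy Endpoint(s).** The statement is repeated: "Data from subjects who do not complete the full study are carried forward in an" intent-to-treat design, and "their data are analyzed using linear mixed models". The sentence just before it says that the analyses take in every subject's assessments. Earlier in section 4.4, the paragraph on alternative or unexpected results describes mixed models as using whatever data are available under intent-to-treat, assuming missingness at random, with auxiliary variables to support that assumption.
- **Research Strategy, Data Analysis.** "Data are assumed to be missing at random; full information maximum likelihood estimators are used, and all data/cases are included in analyses".
- **Section 4.4, General Statistical Approach, repeated under the Go/No-Go heading.** "When appropriate, missing data are handled via multiple imputation or full information maximum likelihood estimation". The Go/No-Go text also limits the Analysis Set for PANSS, MCCB and WHODAS to patients who finished the 30 hours of training and the assessments that follow.

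**The concern.** Next to intent-to-treat and non-completion, carrying data forward is the usual name for filling missed visits with the last available score. On that reading, sessions 20 and 30 and week 12 would already hold values when the mixed model is fitted. Little would be left for a missing-at-random likelihood method to handle, and the model would treat copied scores as fresh observations.

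The Aim 2 questions are whether gains are greater, faster or more durable, and all three concern trajectories. A carried-forward patient contributes a flat line from the last visit onwards. The Aim 2 Go rule is mainly a threshold on an estimated effect size (d of 0.5), so bias in d acts directly on the decision. An analyst who has to choose a reading after seeing the data could affect that decision.

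**Working it through.** **1. The plan's own figure.** Under Power analyses, Aim 1 uses d = 0.5, 80% power, two-sided alpha 0.05 and test-retest correlation 0.8. The change score has variance 2(1 − 0.8) = 0.4 in SD² units. Then n = 2 × (1.960 + 0.842)² × 0.4 / 0.5² = 25.1, so 26 per arm by the normal approximation. With the noncentral t it is 27 (power 81.3%), which matches the stated 27. This figure does not depend on how missing visits are handled.

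**2. Expected non-completion.** The Subject throughput paragraph plans, conservatively, for 18 completers from 27 per arm: 1 − 18/27 = 1/3.

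**3. The two readings against the rest of the text.**

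| Reading | Data Analysis paragraph (missing at random, maximum likelihood, all cases) | Mixed models on available data (section 4.4) | Completers-only Analysis Set (section 4.4) |
|---|---|---|---|
| Missed visits filled with earlier scores | Inconsistent | Inconsistent | Inconsistent |
| Observed data kept in the model | Consistent | Consistent | Inconsistent |

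The Analysis Set sentence conflicts with both readings, so rewording the carried-forward sentences alone would leave a contradiction.

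**4. Size if earlier scores were carried forward, equal dropout.** Assumptions not in the documents: the arm difference grows linearly to 0.5 at session 30, so it is 0.167 at session 10 and 0.333 at session 20. Stopping is unrelated to outcome. With one third stopping in each arm, the expected session-30 contrast is (2/3)(0.5) + (1/3)c, where c is the average carried difference.

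- All stop before session 10: c = 0, contrast = 0.333.
- Stops spread evenly before sessions 10, 20 and 30: c = (0 + 0.167 + 0.333)/3 = 0.167, contrast = 0.389.
- Last score split equally between sessions 10 and 20: c = (0.167 + 0.333)/2 = 0.25, contrast = 0.417.

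A simulation of the evenly spread case (27 per arm, correlation 0.8, 6,000 runs) gave 0.386 with carry-forward and 0.497 with maximum likelihood. With dropout depending on the previous observed score it gave 0.401 and 0.501.

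**5. Unequal dropout.** With evenly spread stops at rate p, the fraction of the full change that survives is f(p) = (1 − p) + (p/3)(0 + 1/3 + 2/3) = 1 − 2p/3. So f(4/9) = 0.704 and f(2/9) = 0.852. Take a gain of 0.65 SD common to both arms. This is borrowed from the verbal-learning effect quoted in the Research Strategy, which is not a primary outcome.

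- True d = 0.5, memantine 4/9 and placebo 2/9: 1.15 × 0.704 − 0.65 × 0.852 = 0.26.
- Rates reversed: 1.15 × 0.852 − 0.65 × 0.704 = 0.52.
- No drug effect: 0.65 × (0.704 − 0.852) = −0.10, or +0.10 with rates reversed. Maximum likelihood gave about 0 in simulation.

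**6. Week 12.** For a patient last seen before session 30, the session-30 and week-12 values are the same copied score. The change between them is zero by construction.

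**7. What these figures are not.** The Aim 2 paragraph of Data Analysis defines the Go criterion as d for the main effect of drug or for drug by session. Under the same linear accrual, the average drug effect over sessions 10, 20 and 30 is (0.167 + 0.333 + 0.5)/3 = 0.333 with no dropout at all. The contrasts in steps 4 and 5 are therefore not operating characteristics of that criterion.

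**The case against.** The strongest answer is that no carry-forward rule exists. The documents never mention a last observation and never say that a missed visit receives an earlier score. What is carried forward is the subjects' data, into an intent-to-treat analysis by mixed models. The neighbouring text in section 4.4 is about including everyone and using available data, and auxiliary variables would have little purpose if the gaps were filled. This stands: a reader might infer that the plan prescribes last-observation-carried-forward, and the text does not establish that.

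Nor can one say that the plan contradicts itself whichever meaning was intended. Keeping observed data is what full-information maximum likelihood does, so that meaning agrees with the Data Analysis paragraph and with the missing-data sentences in section 4.4.

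Other inferences also go too far. The one-third figure is a conservative throughput assumption, not a forecast. It would be wrong to say that patients who stop are never seen at week 12: clinical follow-up of those who exit is pursued to that point, although outcome scoring there is not spelled out. Standard errors that are too small are a plausible consequence of copied scores, but this was not calculated.

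What remains is the wording. If the first half of the sentence means only that data are kept, the second half already says so. Where the authors describe inclusion elsewhere, they do it plainly. The phrase appears twice, once inside the statistical section, and an analyst could reasonably follow it literally.

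**Conclusion.** The wording is ambiguous and should be corrected. Read as carry-forward, it is inconsistent with the missing-at-random likelihood handling and with the description of mixed models on available data. Read as retention, it is a misleading word and no result changes.

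The consequence is conditional. If carry-forward were applied, one third stopped early in each arm and the effect accrued linearly to 0.5, the expected session-30 contrast would be about 0.33 to 0.42. With stopping at 44% and 22% it would be about 0.26 or 0.52, depending on which arm loses more. The direction of bias is therefore not fixed. Accrual, timing, unequal rates and the 0.65 SD common gain are assumptions. A reader might take these figures as the chance of a Go decision; they are not, because the Go criterion is a main effect or an interaction. The Aim 1 sample size is unaffected.

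**What to change.** 1. In the General Clinical Monitoring paragraph and in section 4.4 under Secondary Efficacy Endpoint(s), replace the carried-forward clause with: *are retained: all observed scores from every randomised patient enter the likelihood-based mixed model; no missing score is replaced by an earlier one.*
2. In section 4.4, Go/No-Go decision, change the Analysis Set for PANSS, MCCB and WHODAS to all randomised patients, and keep the completers as a supportive analysis. Without this, the new wording in item 1 would contradict the Analysis Set.

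The sentences that allow multiple imputation can stay; this point does not require them to change. The cost is three edits to the text. No visit, sample size or Aim 1 power figure changes.
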